- 2) concurs that the adult identified is their parent (to also include primary caregivers in the parental role);
- 3) when more than one child in the family falls within the eligible age range, one child will be chosen at random;
- 4) lives in the household at least 4 days a week; and
- 5) sub threshold depressive symptoms (score 6-15) using the CES-DC (child version).

Adolescents will be excluded if:

- 1) they report no or low symptoms (<6) or clinically significant thresholds of depression (16+);
- 2) If any or both in the adolescent-parent dyad are unwilling to consent and/or assent.

Parent inclusion criteria are:

- 1) 18+ years,
- 2) parent or equivalent person responsible (as identified by the household);
- 3) when more than one parent who provides primary care exists in the household, one will be chosen at random to ensure consistency in intervention activities;
- 4) lives in the household at least 4 days a week; and
- 5) sub threshold depressive symptoms (score 0-15) using the CES-D Revised (adult version).

Parents will be excluded if:

- 1) they report clinically significant thresholds of depression (16+);
- 2) If any or both in the adolescent-parent dyad are unwilling to consent and/or assent.

We do not exclude participants based on ethnicity, population, or language groups, but expect that due to the demographics of our study area, we are likely to enroll predominantly isiXhosa, Black African participants. For adolescents, our intervention focuses on preventing HIV risk behavior so adolescents can be sexually active or inactive. We would also like to clarify that our study is not a treatment study and as such, does not enroll psychiatric patients. Instead we focus on individuals that are not meeting clinically significant levels of depressive symptomology based on self-report because this behavioral intervention has a preventive focus. Because we use self-report and non-clinician administered measures to assess possible depressive symptoms, and as such we are not diagnosing mental illness, we will provide a list of clinics where individuals who meet clinically significant levels of depressive symptomology based on self-report so they can be evaluated by mental health professionals. The target population is served by South Africa's public health system, where services are provided for free at point of service.

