## 5. Data Safety and Monitoring

**Data and Safety Monitoring Plan.** Overall internal monitoring of the safety of human subjects will be conducted by PIs. At eligibility screening, those identified with possible clinically significant levels of mental health will be a given list for their nearest mental health service, provided through South Africa's free public health service. This is because this is a prevention study – we offset risk by only including individuals with low levels of depressive symptoms. We screen out those who have progressed to clinically significant ranges. The PIs will oversee monitoring activities. For non-emergency issues, a weekly meeting will be held to address study progress, recruitment and retention, data collection, and other factors related to human subjects and meetings will be held more often if necessary. Emergency protocols will be developed to address serious adverse events and emergency ethical issues should these arise during the intervention or follow-up assessments. Staff will be trained in responses to potential adverse events and given protocol guidelines on how to address these situations. We provide these Standard Operating Protocols or SOPs for review. In cases of adverse events such as identification of depression, suicidal or homicidal ideation, staff will be trained to immediately contact the Project Manager to alert them of the situation. The Project Manager will consult with the PIs to address these issues who are on call at all times during active study recruitment, intervention testing, or assessment. Study staff will be instructed to inform participants they do not have to answer questions that they find too distressing and will be reminded that they can discontinue participation at any time. If needed, participants will be linked to services for stabilization and referral process if they decompensate during eligibility screening, intervention testing, or assessment procedures. Moreover, participants who report significant depression or suicide will not be enrolled in the study (per our exclusion criteria) and will be immediately referred for evaluation and if necessary, psychiatric admission at a local emergency department. Moreover, the Project Manager and PIs should be immediately notified. Participants who develop or report significant depression, suicidal, or homicidal risk during the course of experimental intervention or during assessments will be discontinued and immediately referred for evaluation for psychiatric admission at a local emergency department. All adverse events will be immediately reported to PIs. Serious adverse events will be reported to Brown University IRB/University of Cape Town HREC. A written report will also be given in writing to NIH. All ethical issues will be reported in an annual report to Brown University, University of Cape Town, and NIH.

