**Analysis plan for Aim 1.** We will compare primary outcomes between the two study arms, at 6- and 12-months versus baseline to quantify the intervention's short- and long-term effects. We will compare the continuous and count outcomes (e.g. CES-DC measurement, # of sexual partners, # of sexual episodes without condom) using student's t-test or Wilcoxon rank-sum test (if normality assumption not satisfied), and categorical outcomes (e.g. chlamydia/gonorrhea infection, any STI, frequency of condom use, ever unprotected sex) using Chi-square test or Fisher's exact test (if frequencies are sparse). Changes of outcomes from baseline will be tested using paired t-test, signed rank-rank test, or McNemar's test, whichever is appropriate. For those who are sexually inactive at study enrollment, their sexual debut time will be summarized by Kaplan-Meier curves, and compared using log-rank test. Given that the study has multiple visits, we will use a unified longitudinal model to estimate and draw inference about intervention effects for the primary outcomes. Model (1) is:  $h\{E(Y_{ij})\} = \alpha_i + \beta_1 R_i + \beta_2 R_i \times Time_j + \beta_3 X_i$ , where  $Y_{ij}$  is the outcome at the  $j$ th visit for the  $i$ th individual,  $h(\cdot)$  is a link function,  $\alpha_i$  is a random intercept capturing within-person effect,  $R_i$  represents the treatment group membership,  $Time_j$  codes the study visit, and  $X_i$  denotes baseline covariates. Hence, coefficients  $\beta_1$  and  $\beta_2$  represent the difference between the intervention and control and the effect interaction with time; estimation of the two parameters will be our primary interest. Depending on distribution of primary outcomes, we will choose an appropriate link function for Model (1), e.g. an identity link for CES-DC score, log link for # of unprotected sex, and logit link for any STI. As a result, the interpretation of  $\beta$ s will be mean difference, log(risk ratio), or log(odds ratio). We will compare key baseline variables (e.g. age, gender, socio-economic status) between arms to ensure balance of randomization, and make adjustments in the model (by adding the term  $\beta_3 X_i$ ) to estimate treatment effects as needed. Model (1) will be fit using generalized estimating equations to account for repeated measures. For time-to-sexual debut, we will fit a Cox model among those who are sexually inactive at baseline; Model (2) is:  $\lambda(t; X_i) = \lambda_{0k}(t) \exp(\beta_1 R_i + \beta_3 X_i)$ , where  $\lambda(t; X_i)$  is the hazard of having sexual debut at time  $t$  for the  $i$ th individual and  $\lambda_{0k}(t)$  is the baseline hazard. In this model,  $\beta_1$  is the log(hazard ratio) that captures distributional difference in sexual debut time between study arms. Because time to sexual debut will differ by age, we will fit a stratified Cox model by grouping participants by enrollment age ( $k = 1, 2, 3$  for age=14, 15, and 16) and assuming difference baseline hazard function  $\lambda_{0k}(t)$  for each group. Model (2) will be fit using the partial-likelihood.

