- 4) There is a small risk of ***loss of privacy or confidentiality of data***, including sensitive data on sexual behaviors, substance use, and psychological characteristics. We take this risk seriously, and we will take steps to protect participants' confidential data and anonymity. We will ensure that personal identifiers are never included in any research or analytical datasets, or any publications arising from the study. The informed consent documents will bring confidentiality risks to participants' attention and situations under which disclosure can occur (and to who). Names and any other specific personal identifiers will not be included in any datasets: only a unique participant RIN. Tracking information (including names and telephone numbers) will be available solely to the project staff in charge of planning and organizing follow-up visits. We explain the extensive data protections put into place for our data above (see Data Collection, Management, and Protections). The informed consent and assent documents will highlight confidentiality risks.
- 5) This is *not a treatment study* and as such, does not enroll psychiatric patients. Instead we focus on individuals that are not meeting clinically significant levels of depressive symptomology based on self-report because this behavioral intervention has a preventive focus. *Our study is focused on depression prevention.* We conduct a 'selective' preventive intervention where we are selecting for adolescents at elevated risk for depression onset. We use self-report and non-clinician administered measures to assess possible depressive symptoms (using the Center for Epidemiologic Studies Depression Scale – Revised (version for adults and children, a validated and reliable depressive symptom measure in South Africa),

and as such we are not diagnosing mental illness. However we acknowledge that participants may experience *psychological decompensation*. If this occurs, they will be withdrawn from our prevention focused trial. For these participants, we will provide a list of clinics where individuals who meet clinically significant levels of depressive symptomology based on self-report so they can be evaluated by mental health professionals. The target population is served by South Africa's public health system, where services are provided for free at point of service.

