At eligibility screening, those identified with newly diagnosed HIV and STIs will be offered referral to care and treatment. This process will be repeated at 6- and 12-month follow-up time points. At eligibility screening, participants who report significant depression or suicide will not be enrolled in the study (per our exclusion criteria) and will be immediately referred for evaluation and if necessary, psychiatric admission at a local emergency department. Suicidal admission will result in immediate notification to the Project Manager and PIs. Participants who develop or report significant depression or suicidality during the course of experimental intervention or during assessments will be discontinued and immediately referred for evaluation. Those with clinically significant levels of depression will be given a list for their nearest mental health service (as defined by our reliable, valid symptom measure for depression) provided through South Africa's free public health service. This process will be repeated at 6- and 12-month follow-up time points. This is because this is a prevention study – we offset risk by only including individuals with depressive symptoms below the clinically significant range for depression. We screen out those who have progressed to clinically significant ranges for depression. Standard Operating Protocols have been developed to address serious adverse events and emergency ethical issues should these arise during the intervention or follow-up assessments (see Appendices). Staff will be trained in responses to potential adverse events and given protocol guidelines on how to address these situations. In cases of adverse events such as identification of depression, suicidal or homicidal ideation, staff will be trained to immediately contact the Project Manager to alert them of the situation. The Project Manager will consult with the PIs to address these issues who are on call at all times during active study recruitment, intervention testing, or assessment. Study staff will be instructed to inform participants they do not have to answer questions that they find too distressing and will be reminded that they can discontinue participation at any time. If needed, participants will be linked to services for stabilization and referral process if they decompensate during eligibility screening, intervention testing, or assessment procedures.

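### Model (1) is written with a random intercept but fitted by GEE; if depression-related discontinuation ends follow-up, that fit understates a real CES-DC effect

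*Combined protocol and SAP*

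**What the plan says.** Section 6, analysis plan for Aim 1, sets out one longitudinal model for inference on the primary outcomes, with linear predictor α_i + β1·R_i + β2·R_i×Time_j + β3·X_i. It says that α_i "is a random intercept capturing within-person effect". It chooses links by outcome, "e.g. an identity link for CES-DC score, log link for # of unprotected sex, and logit link for any STI", and then states: "Model (1) will be fit using generalized estimating equations to account for repeated measures". It names no working correlation, weights, imputation or missing-data assumption. Baseline covariates enter as needed for balance, and baseline CES-DC is not named among them.

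The only statement on losses is in Sample Size and Power Considerations, where they count as censoring. That fits time to debut, not Model (1). The only sensitivity analyses mentioned concern mediation.

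The rules on participants who become depressed are spread over several sections:
- Section 5: "Participants who develop or report significant depression, suicidal, or homicidal risk during the course of experimental intervention or during assessments will be discontinued".
- Section D.2, Data and Safety Monitoring Plan: "Participants who develop or report significant depression or suicidality during the course of experimental intervention or during assessments will be discontinued". The same paragraph defines clinically significant depression by the study's symptom measure. It has a service list handed out, and repeats this at 6 and 12 months.
- Section D.1, item 5, on psychological decompensation: "If this occurs, they will be withdrawn from our prevention focused trial".

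The eligibility criteria admit adolescents with CES-DC 6 to 15 and exclude 16 or more. The footnote to the design summary and the Retention paragraph aim to keep participants in follow-up.

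**The concern.** There are two linked problems. First, the equation and the estimator disagree within one paragraph. A random-intercept model has subject-specific coefficients and GEE estimates population-averaged ones. For a binary outcome these are different numbers, and the plan does not say which will be reported. Deleting α_i also leaves no intercept, and the equation has no visit main effect, so it is not yet a complete marginal model.

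Second, adolescents enter just below the clinical threshold, and those who cross it may leave. If they are then not assessed, whether the 12-month CES-DC is observed depends on the 6-month CES-DC, itself a primary outcome measurement. Unweighted GEE is not generally valid under such missingness. If the intervention works, more controls than intervention participants cross the threshold. The remaining controls look better than the whole control arm, and the estimated effect shrinks. At stake are a diluted depression effect, lost power, and an STI odds ratio whose meaning is settled only after the data are seen.

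**Working it through.** **1. Table 1 is not in dispute.** Inputs: 440 per arm, 15% loss, so n = 440 × 0.85 = 374; two-sided α 0.05. Power = Φ[(Δ√n′ − 1.96√(2p̄q̄)) / √(p1q1 + p2q2)], with continuity correction √n′ = √n − 1/(Δ√n) = 19.339 − 0.517 = 18.822.
- CES-DC, 30% v 40%: (1.882 − 1.322)/0.671 = 0.835, power 79.8% (81.9% uncorrected); stated 80%.
- STI, 30% v 20%: (1.882 − 1.200)/0.608 = 1.121, power 86.9%; stated 86%.

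These are two-proportion calculations and do not use Model (1).

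**2. Where the two readings differ.** Take α_i normal with mean μ and SD σ.
- Identity: averaging over α_i gives μ + βR; β is unchanged.
- Log: averaging gives exp(μ + σ²/2 + βR); only the intercept moves.
- Logit: the average of expit(α_i + βR) is not logistic in β, so the odds ratio changes.

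At the plan's 30% v 20%, the marginal OR is (0.20/0.80)/(0.30/0.70) = 0.58, log OR −0.539. The subject-specific ORs giving the same two prevalences (numerical integration, σ assumed) are:

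| σ | log OR | OR |
|---|---|---|
| 1 | −0.631 | 0.53 |
| 2 | −0.844 | 0.43 |
| 3 | −1.106 | 0.33 |

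These are two valid scales. The gap is not a bias.

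**3. Effect of score-driven missingness.** Assumed, not in the documents: scores at baseline, 6 and 12 months normal with mean 10.5, common SD and common correlation; equal effect at 6 and 12 months; 12-month value missing if the 6-month score is 16 or more. From the documents: baseline limited to 6-15. Each run has 30,000 participants. GEE uses all three visits with visit, arm and visit-by-arm, and no baseline covariate. The comparator regresses the 12-month score on baseline and 6-month scores within arm, which is valid when missingness depends on observed scores.

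| SD, corr., effect | Missing, control / intervention | Full data | Independence | Exchangeable | Comparator |
|---|---|---|---|---|---|
| 5, 0.6, −2 | 12.2% / 5.1% | −1.92 | −1.71 | −1.87 | −1.95 |
| 8, 0.3, −4 | 25.8% / 12.5% | −4.01 | −3.65 | −3.81 | −3.99 |
| 8, 0.6, −4 | 22.2% / 8.6% | −3.84 | −3.28 | −3.58 | −3.89 |
| 5, 0.3, 0 | 15.1% / 14.9% | 0.00 | 0.03 | 0.03 | 0.02 |
| 8, 0.6, 0 | 22.6% / 22.6% | 0.01 | 0.10 | 0.09 | 0.15 |

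Largest attenuation: 1 − 3.28/3.84 = 15% (independence) and 1 − 3.58/3.84 = 7% (exchangeable). The smallest came from a further run at SD 5, correlation 0.3, with less unequal missingness (13.4% / 9.1%): full data −2.09, independence −2.00 (4%), exchangeable −2.05 (2%). In the no-effect rows the shifts are within simulation error: in the last row the valid comparator moves by more than either GEE fit.

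For scale, a 12-month arm difference with 374 per arm has an unadjusted standard error of SD × √(2/374): 0.37 at SD 5 and 0.59 at SD 8.

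**4. Does the change of method recover the effect?** Two runs of 200,000 participants used a mixed model with visit, arm-by-visit and baseline CES-DC.
- SD 5, correlation 0.5: full data −1.98; independence −1.76, exchangeable −1.91, mixed −1.98.
- SD 8, correlation 0.6: full data −3.97; independence −3.38, exchangeable −3.69, mixed −3.98.

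A separate run at SD 8, correlation 0.6 splits the gain: full data −4.25, exchangeable −3.93, exchangeable with baseline −4.09, mixed with baseline −4.22. Of the 0.32 shortfall, baseline adjustment recovers 0.16 and the likelihood fit a further 0.13. A random-intercept fit without baseline agreed with exchangeable GEE to within 0.01.

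**5. Weighting.** If everyone at or above the cut-off is unobserved, P(observed | 6-month score ≥ 16) = 0, so a weight of 1/P is undefined. Weights based on the earlier score cannot restore these participants.

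**The case against.** The best defence is that the plan means a marginal model. It writes an expectation not conditioned on α_i, names GEE, and reads the coefficients as a mean difference, log risk ratio or log odds ratio. That is largely right. A reader might infer that the stated effect is the wrong one for every outcome; the documents do not support this. Only the logit outcome is affected, and a marginal odds ratio is a legitimate target. What stands is that α_i is explicitly called a random intercept and that the model without it is incomplete.

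A reader might also infer that the CES-DC estimate is certain to be biased because controls will drop out at 16+. The documents do not establish that either. The 16+ cut-off is stated for eligibility, not discontinuation. Sections 5 and D.2 do not say that assessments stop, and the latter repeats its referral step at 6 and 12 months. The word withdrawn in D.1 is tied to decompensation, not to a score. If assessments continue, the missing-data part largely falls away.

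Nor is GEE as such the culprit. It tolerates missingness that depends on modelled covariates, and about half of the gain in step 4 comes from adding baseline CES-DC. With exchangeable correlation at SD 5 the loss is 0.07 points (1.98 − 1.91), small beside a standard error of 0.37. But the plan specifies neither exchangeable correlation nor baseline CES-DC. At SD 8 under independence the loss is 0.59 (3.97 − 3.38), about one standard error.

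**Conclusion.** The concern holds in a limited form. Model (1) and its fitting method are inconsistent as written, and this changes the reported number only for the logit outcome: 0.58 marginal, against 0.53 to 0.33 subject-specific for assumed intercept SDs of 1 to 3.

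Conditionally on discontinuation ending follow-up, unweighted GEE without baseline CES-DC understates a true 12-month effect by roughly 2-7% (exchangeable) or 4-15% (independence). Those figures rest on assumed SDs of 5 to 8, correlations of 0.3 to 0.6, effects of about −2 to −4 points and a 16+ trigger borrowed from eligibility. They are illustrative.

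A reader might fear a false claim of benefit. The calculations do not show one: with no effect, withdrawal is equal in the two arms and no clear bias appears. The harm is dilution and lost power. No sample size or power figure changes.

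**What to change.** - **CES-DC:** fit a likelihood-based linear mixed model to the post-baseline visits with visit, arm, arm-by-visit and baseline CES-DC.
- **Binary and count outcomes:** drop α_i, add an intercept and a visit main effect, and present Model (1) as a marginal GEE model with a stated working correlation, robust standard errors and adjustment for the baseline value. Report the odds ratio as marginal.
- **Missing data:** state the assumption. Use multiple imputation from earlier scores, with a sensitivity analysis for departures from it. Do not rely on inverse-probability weights based on the earlier score.
- **Consistency:** the design-summary footnote, the Retention paragraph and sections 5, D.1 (item 5) and D.2 must be reconciled on whether discontinued participants are still assessed.

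The cost is a few paragraphs of analysis text and standard software, with no change to sample size or visits. The downside is that the mixed model and the imputation rely on distributional assumptions. If nobody above the cut-off is observed at 12 months, both extrapolate beyond the observed scores, which is why the sensitivity analysis is needed.

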policy relevance, and strike a balance between costs while protecting the integrity of our main scientific goal, to have enough power to thoroughly examine the main outcomes.

**Sample Size and Power Considerations.** We use data from our preliminary pilot study and other relevant secondary sources to formulate a realistic range of necessary assumptions for sample size and power considerations for primary outcomes. As shown in Table 1 we estimate that a total sample size of 880 adolescents, or 440 adolescents per arm, will be required to adequately power our study.

[figure not shown]

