### **3. Recruitment and Enrollment**

**Recruitment setting and procedures.** Our trained bi-lingual study team will recruit.

For Aim 1 (efficacy trial), we will recruit N=880 adolescents (and N=880 parents) to test *Our Family Our Future* (described above) in a fully-powered RCT. We will recruit in person through the Masiphumele community site and in the community. We use a recruitment strategy based on "approach all" in both the Masiphumele Community Center (run by the Desmond Tutu HIV Foundation) and surrounding community to limit bias and combat stigma. In the community, we recruit based on procedures used in the preliminary studies. This includes splitting the

Masiphumele community into census enumeration size areas, randomly selecting one area to begin to limit geographical bias. Then, we will systematically recruit by going door-to-door, approaching all for study information and eligibility screening. We visit homes up to 3 times at different times and days to limit day/time bias.

For Aim 2, we do *not* recruit any new participants. This aim is analytical, focusing on the data that was collected in Aim 1.

For Aim 3, For Aim 3 (qualitative component), we recruit a convenience sub-sample of adolescents and parents who were randomized to the intervention arm for in-depth interviews, based on prior participation in the efficacy trial (Aim 1) since planned qualitative interviews in Aim 3, explore the experience of the intervention. The recruitment, consent and assent process for adolescents and parents was described under Aim 1. For stakeholder in-depth interviews, we will recruit individuals that can provide insight into future implementation of the intervention (including intervention facilitators) as well as individuals that may have a stake in future scale-up and implementation of the intervention if shown to be efficacious such as possible future interventionists, program directors, and leadership at DTHF. Stakeholder participants will be recruited through flyers providing contact details for study staff in the community organization work areas. We will also recruit using an initial participant seed pool as recommended by Drs. [name] and [name]. These stakeholders will identify other stakeholders. Staff will speak to interested stakeholders privately by phone or in person. Then study staff will obtain informed voluntary consent.

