
**Question 2:** What mediates and moderates the effect of the intervention on the main outcomes?

Figure 2. Causal pathway illustrating the hypothesized relationships between intervention (I), intermediate factors (IF) and outcomes.

**Mediation Analysis.** We will investigate theoretically-derived mediators proposed to explain the efficacy of *Our Family Our Future* on prevention of HIV/STI acquisition, reducing HIV/STI risk behavior, and reductions in depressive symptoms. Specifically, we examine whether the extent of impact of *Our Family Our Future* on outcomes is mediated by changes in resilience; behavioral skills and efficacy (e.g., condom use, sex refusal); norms and attitudes relating to sex, condom use, gender; family interactions; and social support. Let us denote these potential mediators as intermediate factors (IF).

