Our hypothesis is that beside a direct effect on the primary outcome, the intervention can cause changes in these IF at 6-months, which ultimately lead to change in primary outcomes at 12-months. Figure 2 depicts three candidate submodels, using directed acyclic graphs, to represent hypothesized causal pathway leading from intervention to primary outcomes. The full mediation model is given in Figure 2(c), which fully decomposes the effect of the intervention, but contains multiple pathways whose effects are not simultaneously estimable from a single regression model. We will proceed by fitting the following submodels, which we expect will indicate the role of mediators in explaining the effect of our intervention. The time ordering of data collection gives us an excellent opportunity to untangle relationships using causal mediation analysis. Submodel (a) describes the causal effects on intervention on the IF and primary outcomes. Given the study intervention is randomized, this submodel is identified by data. Submodel (b) focuses on the causal effects on intervention and IF on the primary outcomes. The effect of IF in Submodel (b) is subject to confounding, and hence its estimation will be based on certain model assumptions (e.g. sequential ignorability). Estimates of submodels (a) and (b) will generate a rough idea of the relative degree to which intervention effect is mediated by each of IF. If the two models suggest a causal relationship between intervention and an IF and between IF and primary outcomes, its mediation effect will be considered in the full model (c) that describes the full process. Thus from analyses of submodels (a) and (b), we will select the best candidate variables with the strongest mediation effects from intervention to IF, and from IF to the outcome. Statistical modeling will utilize causal mediation models, fit using a weighted two-stage regression approach implemented with SAS macros to estimate the full model (c). For our mediation analysis, we will focus on direct and indirection *natural* effects.

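### Mediators are picked for strength and then estimated on the same participants, so the selected indirect effects tend to be overstated and their 95% intervals under-cover

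*Combined protocol and SAP*

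**What the plan says.** Mediation is the first half of Aim 2 and part of one of the three primary study questions. Section 6 (Mediation Analysis) lists five domains of intermediate factor (IF): "resilience; behavioral skills and efficacy (e.g., condom use, sex refusal); norms and attitudes relating to sex, condom use, gender; family interactions; and social support". The hypothesis is that "the intervention can cause changes in these IF at 6-months, which ultimately lead to change in primary outcomes at 12-months".

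The procedure has three steps. Submodel (a) estimates the effect of the intervention on each IF and on the outcome. Submodel (b) estimates the effect of the intervention and IF on the outcome. If both point to a causal path for an IF, "its mediation effect will be considered in the full model (c) that describes the full process". The next sentence sums up the rule: "we will select the best candidate variables with the strongest mediation effects from intervention to IF, and from IF to the outcome". Model (c) is then fitted by weighted two-stage regression with SAS macros.

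Section 3 says of Aim 2 that "This aim is analytical, focusing on the data that was collected in Aim 1", so no new participants are recruited and no hold-out sample is described. The plan gives no threshold for the screen, number of mediators to keep, sample split, interval method, multiplicity control or commitment to report the candidates that were not selected.

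**The concern.** A variable that looks strongest in a set of estimates owes that place partly to its true effect and partly to favourable error. If its effect is then estimated from the same people, the favourable error stays in. The estimate is biased away from zero, and an interval that ignores the search is centred in the wrong place.

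Aim 2 is meant to say how the intervention works and so to guide later adaptation and scale-up. At stake is whether a chance pathway is reported with an interval that does not show how it was found, and whether a real pathway is credited with more of the effect than it carries.

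**Working it through.** **Inputs.** From the documents: "we estimate that a total sample size of 880 adolescents, or 440 adolescents per arm", two-sided alpha 0.05 and 15% loss to follow-up (Section 2, Sample Size and Power Considerations). Analysed N = 880 × 0.85 = 748, or 374 per arm. The documents do not give the number of candidates K, the path strengths or the correlations between mediators. These are assumptions and are varied below.

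**The plan's own figure.** No power or precision figure is given for mediation. Table 1 serves only to confirm the analysed N. For HIV/STI at 30% vs 20%, the continuity-corrected effective size per arm is (374 − 1/0.10)²/374 = 364²/374 = 354.3. Then z = [0.10 × √354.3 − 1.96 × √(2 × 0.25 × 0.75)] / √(0.21 + 0.16) = (1.882 − 1.200)/0.608 = 1.12, a power of 86.9% against the stated 86%. So 374 per arm is the right basis.

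**Why selection inflates, in one line.** With unit SD, the standard error of the intervention effect on a mediator is √(2/374) = 0.073, so passing a 5% screen needs an estimate beyond 1.96 × 0.073 = 0.143 SD. A mediator truly shifted by 0.10 SD can pass in the right direction only if that path is overestimated by at least 0.143/0.10 = 1.43-fold.

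**How many candidates?** The mediator and moderator row of Table 2 lists about 25 instruments, but many lie outside the five mediator domains (anxiety, trauma, stigma, alcohol, drugs). About 11 fall within them: resilience 1, social support 1, condom attitudes, efficacy and skills 3, family 6. K from 5 to 20 brackets this.

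**Simulation with real effects.** n = 748, 1:1, continuous variables, product-of-coefficients indirect effect, 95% Monte Carlo interval. Path sizes are drawn as |N(0, τ)|, with 30% of each path set to zero. Both paths are screened at p < 0.05, up to three of the strongest are kept, and effects are estimated on the same data. Ranges are over K = 5, 10, 20.

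| τ for the two paths | Estimate/truth | 95% coverage | Split-half: estimate/truth | Split-half: coverage |
|---|---|---|---|---|
| 0.10, 0.05 (weak) | 2.16 | 0.755–0.771 | 0.91–1.04 | 0.979–0.983 |
| 0.20, 0.10 (small) | 1.27–1.28 | 0.875–0.884 | 0.99–1.02 | 0.953–0.954 |
| 0.30, 0.15 (moderate) | 1.11–1.12 | 0.891–0.911 | 0.99–1.00 | 0.948–0.953 |

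With no selection the ratio is 0.93–1.06 and coverage 0.965–0.989, so the selection causes the bias. If only the single strongest of equal mediators is kept, the ratio is 1.23–3.68 at K = 5 and 1.38–3.91 at K = 20, with coverage 0.90–0.94 and 0.66–0.84.

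**Simulation with no effect on any mediator.** The candidate with the largest |a × b| is tested with a delta-method interval. All candidates are in one outcome regression.

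| Mediator–outcome path | Correlation among mediators | Falsely significant, K = 6 to 20 |
|---|---|---|
| 0.3 per SD | 0 | 23%, 35%, 55% (K = 6, 10, 20) |
| 0.3 per SD | 0.5 | 13% to 31% |
| 0.1 per SD | 0 | 5% to 17% |
| 0.1 per SD | 0.5 | about 2% to 5% |

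One mediator fixed in advance gives 4.5% in the first setting. False-discovery-rate control over all candidates brings that setting's rates to about 2% to 4%. The last row depends on the joint regression. Fitted one at a time, each mediator borrows from the others, with slope b[1 + (K − 1)ρ] = 0.1 × (1 + 5 × 0.5) = 0.35 per SD at K = 6, so that row should not be taken as reassurance for one-at-a-time screening.

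**The case against.** The strongest reply is that the selection sentence only restates the two-path gate before it. It keeps variables in the plural and need not rank them to a single winner. Read that way, the step is a significance screen, and for equal true effects the simulated ratio is 1.02 at paths of 0.3 and 0.15, 1.00 for stronger paths, and coverage is 0.95 to 0.98. This stands as far as it goes. But the text does speak of the strongest, and the screen alone still inflates weaker effects (about 1.55-fold for small and 3.5-fold for weak paths). The plan gives no ground for assuming that mediator effects are moderate or larger.

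A second reply is that the candidates come from theory: "We will investigate theoretically-derived mediators proposed to explain the efficacy". That limits the pool but not the data-driven choice within it.

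A third is that the plan is already cautious. It treats the submodels as giving only an approximate picture, admits that methods for several mediators are limited, and closes its limitations by looking to later confirmatory work. That closing sentence follows one on moderation power, so its scope is arguable, but it can fairly be read to cover mediation. A reader might infer that selected pathways will be presented as confirmed, and the documents do not support that. The caveat is still not a correction, and the sensitivity analyses concern unmeasured confounding.

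Other stronger readings also fail:
- That the intervals are too narrow. They are misplaced, not shorter.
- That naive standard errors are planned. No interval method is named, which is a gap and not a stated error.
- That more than 20 mediators will be searched. The Table 2 row mixes mediators and moderators.
- That the search runs over four outcomes. The mediation text names three targets: HIV/STI acquisition, risk behaviour and depressive symptoms.

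**Conclusion.** The concern holds for Aim 2. Followed as written, the plan selects and estimates on the same 748 or so participants with no allowance for the selection. Selected indirect effects will tend to be overstated, and nominal 95% intervals will under-cover.

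The size cannot be fixed from the documents. With real effects and up to three mediators kept, inflation is about 1.1- to 2.2-fold. With no effect on any mediator, the false-positive rate runs from about 2% to 55%. The figure of 55% is one end of that range: it needs 20 uncorrelated candidates, each related to the outcome at 0.3 per SD. It is close to, and below, the plain multiplicity rate 1 − 0.95^20 = 64%, so it reflects the number of tests as much as inflation of a chosen effect. Correlated scales and weaker paths lower it. The simulations use continuous variables and a product of coefficients, a simplification of the planned natural-effect models.

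A reader might infer that the efficacy results are also in doubt. They are not: the Aim 1 comparisons and Table 1 do not depend on this step. It is a worthwhile improvement and not a threat to the trial's main conclusion.

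**What to change.** Preferably, name in advance the scales that enter model (c) for each outcome, chosen from the five domains, and fit model (c) with those whatever submodels (a) and (b) show.

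If selection is kept:
1. State the rule: the threshold on each path, how strength is ranked, and how many variables are kept.
2. Report the indirect effect of every candidate, with false-discovery-rate control across candidates.
3. Estimate the selected mediators and their intervals by sample splitting or cross-fitting. A bootstrap that repeats the selection in each resample is a weaker alternative, because its intervals need not be re-centred on the truth.
4. Label the selected pathways exploratory.

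In either case, name the interval method for model (c).

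The cost is analysis wording and computing time, with no new data. The price is precision and fewer claimed mediators: with moderate effects and K = 10, the mean interval width rises from 0.075 to 0.109 under split-half estimation, a factor of 0.109/0.075 = 1.45. Naming mediators in advance avoids that loss but gives up the chance to promote an unexpected candidate.
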